All RCT participants will be paid a modest amount to compensate for time and travel to research assessments. Participants will be reimbursed uShs 55,887 (approximately US\$15) for each quantitative screening, baseline, and 13-week interview and uShs 74,516 (approximately US\$20) for the final (6-month) interview and for each qualitative interview.

The patient study participants will not receive compensation for attendance at the TEAM or ETAU sessions, however they will receive modest compensation for the travel costs required to arrive/depart from the TEAM or ETAU session. Care partners/family members of patient participants will also receive modest compensation for the travel costs to arrive/depart from the TEAM or ETAU sessions. Health clinic staff will receive modest compensation for the time required to participate in a single focus group on TEAM process measures.

Peer educators will receive uShs 22,355 (approximately US\$6) for each TEAM session and for each TEAM training session that they attend.

Provisions to Monitor the Data to Ensure the Safety of Research Participants

The study PIs, Drs. [name] and [name], will monitor the study to ensure data integrity and the safety of the participants. The MakCHS site Data Coordinator, will review the data for discrepancies on a regular basis and will review the study records for compliance with IRB requirements and verification of source documents. Ugandan investigators and research staff will be responsible for all stages of the project: recruiting and consenting participants, conducting the surveys, qualitative interviews, and conducting all study assessments. They will be responsible for all data collection. Management of data will take place at MakCHS, but de-identified data will be transferred to CWRU for final analysis.

The data safety and monitoring plan for this project consists of several components, as outlined below. The PIs ([name] & [name]) will be responsible for ensuring that this plan is followed during the course of this study.

1. Approval from the Case Western Reserve University (CWRU) Institutional Review Board (IRB) and from the Makerere College of Health Sciences (MakCHS) IRB will be obtained prior to performing any research related to this study and approval will be maintained throughout the study period via continuing review.
2. Drs. [name] & [name] will conduct regular research staff meetings to closely monitor study start-up and progress, including oversight of staff training and research capacity building. As was done in the Neurology MEPI and in the R21 pilot study, meetings that involve both Ugandan and U.S. study team members will be held via web teleconference. Meeting minutes will be sent to research staff participants. More frequent local meetings and ad-hoc full team meetings that may be called in the event that problems or concerns arise during the study period will supplement the regularly scheduled web calls.
3. There will be at least 2 in-person visits to the sites annually by the U.S. PI.
4. **Adverse event identification/classification:** The study investigators and/or qualified research assistants will identify adverse events. All adverse events, whether considered serious or not, will be recorded and reviewed by the study PIs on an ongoing basis, and reported to the IRB according to local IRB policy. Serious adverse events are defined as events that result in any of the following: death; a life threatening experience; inpatient hospitalization or prolongation of existing hospitalization; a persistent or significant disability/incapacity; or a congenital anomaly/birth defect (or an event that may require

medical or surgical intervention to prevent one of the outcomes listed above). Strokes will be recorded if/when they occur and will be considered serious adverse events. All adverse events, including all serious adverse events, will be reported to the IRB according to local IRB policy and to the Data Safety and Monitoring Board (DSMB). A summary report of all adverse events will be submitted to NINDS annually, and at the end of the study.

5. **Data and Safety Monitoring Board (DSMB) and safety review plan:** We recognize the need for careful, expert external data and safety oversight to ensure the wellbeing of the participants in this study and the scientific integrity of the project. These experts, who are not members of the study team, will review and evaluate the accumulated data for participant safety, adverse events, study conduct and progress, at minimum, every 12 months. Ad-hoc meetings might be called to evaluate unanticipated serious adverse events or any other urgent issues that are relevant and which might occur during the course of the study. The DSMB will be comprised of two clinicians with stroke expertise at the Uganda site; a faculty member/clinician with stroke expertise at the US site, and a biostatistician at the US site who are all not part of the study team, but have extensive experience with federally funded research. The DSMB communication and oversight will be accomplished via telephone, SKYPE, or email communication for issues that need more immediate attention.

The PIs will review study progress and safety regularly as described above. As noted above, progress reports, including patient recruitment, retention/attrition, and adverse events will be provided to the DSMB at least annually for independent review. The annual report will include a list and summarization of adverse events. In addition, the annual report will address (1) whether adverse event rates are consistent with pre-study assumptions; (2) reason for dropouts from the study; (3) whether all participants met entry criteria; (4) whether continuation of the study is justified on the basis that additional data are needed to accomplish the stated aims of the study; and (5) conditions whereby the study might be terminated prematurely. There will be an interim analysis conducted once half of all trial participants have completed the 6-month outcome evaluation point. The annual report will be signed by the PI/designate and will be forwarded to the DSMB. The DSMB will review the annual plan on all 5 points outlined above, as well as the interim analysis, and make recommendations to the appropriate regulatory agencies (IRB, NIH) concerning continuation, modification or termination of the study. The PI will provide a copy of all DSMB reports to the appropriate IRB and NIH on an annual basis.

Data Analysis Plan

Quantitative data Analysis: Preliminary descriptive analyses will examine change over time in systolic BP as well as secondary outcomes. The measures of interest are valid and reliable, and have been used in stroke studies in the SSA setting.^{24, 30, 88, 97, 98} Primary and secondary outcome measurements will be assessed at baseline prior to randomization to either TEAM or ETAU, and at the 13 week and 6 month time-points using the same methods as in our pilot work. Of primary interest is the treatment by time interaction in systolic BP, measured from baseline to 6 months after randomization between TEAM and ETAU. Explanatory variables will include age, gender, stroke history and rural vs. urban status.

The 13-week systolic BP measurement will reflect the period following baseline (when individuals participating in TEAM Uganda will have just completed the “intensive” group sessions), and it will be used to assess for within-subject differences from baseline to 13 weeks and 13 week to 6-month time periods. This will allow for a greater understanding of the time course for when the expected reductions occur in the TEAM Uganda group, which we expect to mostly occur after the “intensive” group sessions have ended. We will analyze change from baseline to 13 weeks as well, analyzing contrasts within the mixed model framework.

For aim 2, we will use 2 group by 3 time waves repeated measures analysis of variance (RMANOVA) for each of the 3 hypotheses in Aims 2. These analyses will compare two groups (TEAM intervention vs. enhanced treatment as usual (ETAU)) across three time waves of systolic BP (H1), serum cholesterol (H2), and serum HbA1c (H3). When using a repeated measures ANOVA, it not only assesses mean differences across time, but also assesses group differences, as well as, the interaction of time X group which will allow us to test the trend of the means over time across the three groups. The repeated measures ANOVA, not only can be used to determine if there are mean differences across the three time periods, it can also utilize orthogonal polynomial contrasts to determine linear and quadratic trends of the means across time. Orthogonal polynomials are weights

assigned to each time period that model a linear or quadratic (non-linear) trend. Repeated measures ANOVA can determine if these trends in the means are significant. A linear trend is indicated if there is a steady increase or decline in scores from the first time wave to the third time wave. A quadratic trend is indicated if there is a change in direction based on scores across the time waves. For example, if there is a decrease in mean scores from T1 (baseline) to T2 (13 weeks), but an increase in scores at the T3 (6 months), this would be indicative of a U trend for the three time periods and a return toward the mean score from T1 to T3. A quadratic trend can also indicate a single change in direction in the trend of the means, for example, if there is a decline in means scores from T1 to T2, and the decreased mean score is maintained at T3. The major assumption to be tested with repeated measures ANOVA is sphericity. Sphericity is a form of compound symmetry and refers to the equality of variances of the differences between each time wave.⁹⁹ If the assumption of sphericity is violated based on the Mauchly's test, SPSS provides an adjusted F, df, and p-value in repeated measures ANOVA to account for this violation. We may also explore repeated measures mixed model approaches to analyze change from baseline to 13 weeks as well, analyzing contrasts within the mixed model framework.

Secondary outcomes: We will model secondary outcomes over time in a similar manner. We will consider generalized linear models when distributions of outcomes are not approximately normally distributed, or transformations of outcome variables to normality. We will also conduct exploratory moderator analyses of the explanatory variables in the primary mixed model. Mediation analyses also will be explored. Potential mediators include dose of TEAM session exposure, medication prescription/access and adherence to a heart healthy diet. Variables with (change) values that appear to be associated with change in systolic BP levels and that appear to differ by treatment will be considered further as mediator variables, following as in MacKinnon (2008)¹⁰⁰ and Preacher and Hayes (2008).¹⁰¹ This will involve single mediator analyses as well as multiple mediator models. These analyses will involve the treatment variable and change in systolic BP values. Associated standard errors of estimated indirect effects will be derived through bootstrapping, using the M-Plus software.

Sample size calculations: From our pilot data, mean baseline systolic BP was 162.9 (SD 25.6). Change from baseline to 6 months with the TEAM Uganda intervention saw a mean systolic BP of 149.7 (SD 22.1). Reductions BP of ≥ 2 mm Hg can significantly reduce the incidence of cardiovascular disease and its complications in both hypertensive and normotensive individuals, and reductions of the magnitude seen in this team's pilot work is well above thresholds that are considered clinically meaningful.^{94, 95} Our projected sample size is n=246, with 123 participants per arm. Based on our preliminary mixed model, we observed difference in systolic BP from baseline to 24 weeks of 13.22, with standard deviation of 25.84, and within subject correlation parameter value of 0.57. However, we will conservatively estimate our sample size based upon a difference of 10 mmHg, commensurate with a meta-analysis that used this magnitude of change in BP across a large sample with varying baseline blood pressure levels and comorbidities.⁹⁶ Also in our pilot work with the TEAM Uganda study, we observed an attrition rate of 12.5% at 6-months follow-up. Conservatively, for this study, we will assume 25% attrition. Finally, to assume for two-sided test of time-by-treatment group interaction, Type I error level is 0.05. Then, in a linear mixed model with subject-level and center-level random effects, power is 0.80 for a clinically significant difference of 10.0 mm Hg between treatment arms for the projected sample size of 246 subjects in total. We should thus have sufficient power. We do assume compound symmetry over the 3 time periods. We will also consider an AR(1) covariance model, and compare model fits.

Missing Data: Strategies to minimize loss to follow-up are outlined in Form E, specifically the description of our Recruitment and Retention Plan. Data that remain missing despite our retention efforts will be accommodated in our analyses and their impact evaluated through sensitivity analyses. The models we propose can be estimated without bias under the missing at random (MAR) assumption¹⁰² and provide valid analysis as long as covariates associated with missingness (if any) are included in the mixed model. To assess which covariates may be associated with missing outcome data, we will create binary indicators of whether the outcome was missing (=1) or not (=0). If a covariate is correlated with missingness at $r > 0.40$ and is correlated at $r > 0.40$ with the original response variable, it will be included in the analysis as an auxiliary correlate.¹⁰³ We will conduct assessment of the missing at random (MAR) assumption by pattern mixture models that relax the missing at random assumption, while analyzing the sensitivity of treatment by time interaction effects. . We will also consider using Full Information Maximum Likelihood models in presence of incomplete data.¹⁰⁴

Qualitative data analysis plan: PIs at each of the proposed study sites will be responsible for overseeing data input and quality

Two qualitative researchers will be used to ensure standardization of qualitative analysis. The qualitative team will first independently review each transcript and highlight significant statements, sentences, or quotes. Based on review of the independently derived statements, the team will develop consensus-based “clusters of meaning”¹⁰⁵ or relevant “themes and categories”.¹⁰⁶ Each researcher will further read/code each document independently and iteratively until no new insights emerge. Initial codes will be recorded using NVivo. These entries will be elaborated as coding progresses. The qualitative researchers will then construct a consensus-based coding dictionary that includes mutually exclusive definitions for each code. This coding structure will be reviewed after a preliminary analysis of a sub sample of transcripts, and the dictionary will be refined through comparison, categorization, and discussion.^{106, 107} Although code definitions are mutually exclusive, the same portions of text can be attached to multiple codes. The refined codes will then be applied to the transcripts, with coding decisions recorded electronically using NVivo. All transcripts will be coded by both qualitative researchers. In our previous research, checks for inter-rater consistency using Cohen’s Kappa¹⁰⁸ yielded Kappa $\geq .90$ which was considered excellent agreement.

NVivo will be used to retrieve all segments of text attached to a particular code to create code-based files across all respondents. The qualitative team will further elaborate, refine, and differentiate the codes and identify similarities and differences through comparison of respondents. Emergent observations will be recorded in theoretical memos using NVivo’s Project Document feature. This process of engagement with the data and iterative discussions will be repeated until all discrepancies are resolved and no new insights emerge.

Table 1: RCT Schedule of study events

	Screen	Baseline	Wk 1-12	Wk 13	Wk 13 - Mth 6	Mth 6	Mth 12
PROCEDURES							
Identification of participants: Inclusion/Exclusion criteria review	X						
Informed Consent	X						
Demographics	X						
Medical Status & Burden: Self-reported Charlson Comorbidity Index Medications Personal and family stroke history		X					
Randomization		X					
Primary Outcome: Systolic BP	X		X		X		
Secondary Outcomes:							
Diastolic BP							
Serum cholesterol							
HbA1c							
Serum HDL, LDL, triglycerides							
BMI							
Diet questionnaire			X				
GPAQ				X			
GATS					X		
AUDIT						X	
General self-efficacy							
Stroke knowledge							
INTERSTROKE stress							
Medication adherence (MARS)							

Medication Access						
Health resource use						
Qualitative Assessment						
Patient		X		X		
Clinicians/Administrators				X*		
SAB**						
Intervention attendance			X			
Enduring effects of the intervention						X

* Clinicians who refer patients will be assessed when their patient reaches the 6-month time-point. A sample of clinician/ administrators will be assessed in Year 4 to assess overall value/alignment of the intervention.

** The SAB will be assessed in Year 5.

References

1. Feigin, V.L., et al., *Global and regional burden of stroke during 1990-2010: findings from the Global Burden of Disease Study 2010*. Lancet, 2014. **383**(9913): p. 245-54.
2. Chin, J.H., *Stroke in sub-Saharan Africa: an urgent call for prevention*. Neurology, 2012. **78**(13): p. 1007-8.
3. Beaglehole, R., et al., *UN High-Level Meeting on Non-Communicable Diseases: addressing four questions*. Lancet, 2011. **378**(9789): p. 449-55.
4. Strong, K., C. Mathers, and R. Bonita, *Preventing stroke: saving lives around the world*. Lancet Neurol, 2007. **6**(2): p. 182-7.
5. Organization., W.H., *Global burden of disease (GBD) 2002 estimates*. 2004: Geneva, Switzerland.
6. Connor, M.D., et al., *Burden of stroke in black populations in sub-Saharan Africa*. Lancet Neurol, 2007. **6**(3): p. 269-78.
7. O'Donnell, M.J., et al., *Risk factors for ischaemic and intracerebral haemorrhagic stroke in 22 countries (the INTERSTROKE study): a case-control study*. Lancet, 2010. **376**(9735): p. 112-23.
8. Organization., W.H., *Global Burden of Disease (GBD) 2004 update*. 2008, WHO: Geneva, Switzerland.
9. Truelsen, T., *Stroke incidence studies in Africa*. Lancet Neurol, 2010. **9**(8): p. 755-7.
10. Adeloye, D., *An estimate of the incidence and prevalence of stroke in Africa: a systematic review and meta-analysis*. PLoS One, 2014. **9**(6): p. e100724.
11. Walker, R., *Hypertension and stroke in sub-saharan Africa*. transactions of the Royal Society of Tropical Medicine and Hygiene, 1994. **88**: p. 609-611.
12. Forouzanfar, M.H., et al., *Global Burden of Hypertension and Systolic Blood Pressure of at Least 110 to 115 mm Hg, 1990-2015*. JAMA, 2017. **317**(2): p. 165-182.

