2.	At risk for stroke defined by the following: a.) High systolic BP defined as ≥ 140 mmHg assessed on at least 2 occasions at least 3 days apart and either criterion b or c as noted below: b.) At least 1 other modifiable stroke risk factor including: diabetes, hyperlipidemia, obesity, smoking, problem alcohol use or sedentary lifestyle. Problem alcohol use for screening purposes

	
will be assessed with questions on frequency, type of alcohol and quantity consumed. Participants will be classified as engaging in potential problem alcohol use if they exceed the recommended level for safe alcohol intake i.e. more than 3 drinks on average every time they drink, or if they undertook binge drinking (i.e. more than 3 drinks on one occasion in the one month preceding the evaluation).^{70, 71}
 
c.) History of stroke or transient ischemic attack within the past 5 years

3.	Able to participate in group sessions
	Inclusion Criteria for Care Partner participant
1.	Age range: from 18 to 90
2.	Able to participate in group sessions
	Inclusion Criteria for Peer Educator
1.	Age range: from 18 to 90
2.	
At risk for stroke defined by the following:
 
a.) High systolic BP defined as ≥ 140 mmHg assessed on at least 2 occasions at least 3 days apart and either criterion b or c as noted below:
 
b.) At least 1 other modifiable stroke risk factor including: diabetes, hyperlipidemia, obesity, smoking, problem alcohol use or sedentary lifestyle. Problem alcohol use for screening purposes will be assessed with questions on frequency, type of alcohol and quantity consumed.
 
Participants will be classified as engaging in potential problem alcohol use if they exceed the recommended level for safe alcohol intake i.e. more than 3 drinks on average every time they drink, or if they undertook binge drinking (i.e. more than 3 drinks on one occasion in the one month preceding the evaluation).^{70, 71}
 
c.) History of stroke or transient ischemic attack

3.	Able to participate in group sessions
	Inclusion Criteria for Peer Educator Care Partner
1.	Age range: from 18 to 90
2.	Able to participate in group sessions
	Inclusion Criteria for Clinic Staff
1.	Member of clinic and administrative staff (whether they referred participants to study or not) at the 3 sites (physicians, nurses, health workers, pharmacists).

	Exclusion Criteria for RCT participant
1.	Individuals who are unable or unwilling to provide written informed consent

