Measures: Demographic variables and existing medical burden (assessed with the self-reported Charlson Index⁷⁹) will be evaluated at baseline, prior to study randomization. Baseline medical status will also be evaluated with personal and family stroke history as well as currently prescribed medications. Primary outcome of the RCT will be change in systolic BP from baseline to 6-month follow-up. Additional outcomes of interest will include diastolic BP, cholesterol/lipids and glycosylated hemoglobin (HbA1c) (approximately 5mL of blood is drawn per blood draw), body mass index (BMI), measures that evaluate diet, activity levels, substance use, self-efficacy, stroke knowledge, stress, medication adherence, medication access and health resource use. Quantitative measures will be repeated at 13-week and 24-week (6-month) follow-up except for laboratory testing, which will be conducted only at baseline and 24-week follow-up. Qualitative evaluation will be conducted at baseline and at 13-week follow-up.

[figure not shown]
Primary outcome: The primary study outcome is systolic BP measured at baseline, 13-week, 24-week (6 month). All BP measurements will adhere to a standardized procedure previously used by this study team.³⁰ Prior to BP measurement study participants will be requested beforehand to refrain from smoking and drinking alcohol or caffeinated beverages at least half an hour before the examination. BP will measured with an Omron automated sphygmomanometer model HEM 907 whose accuracy has been validated.⁸⁰ The participant will be asked to sit on a chair and rest quietly for 15 minutes with his/her legs uncrossed. The left arm will then be placed on a table with the palm facing upward and the ante-cubital fossa at the level of the lower sternum. Two arm cuffs that fitted arm circumferences 9-13 inches and 13-17 inches will be available for use in BP measurement. Three measurements will be taken at least 5 minutes apart. The average of the last two readings will be considered as the final blood pressure reading.

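### Screening systolic BP, required before randomisation, is not used in the H1 analysis: a small, avoidable loss of precision (minor)

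*Combined protocol and SAP*

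**What the plan says.** Criterion 2a for RCT participants (Inclusion and Exclusion Criteria) requires "High systolic BP defined as ≥ 140 mmHg assessed on at least 2 occasions at least 3 days apart". The paragraph on RCT treatment randomization places allocation after all screening and baseline procedures, and the schedule of study procedures lists screening and baseline as separate assessments.

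Under Measures, "Primary outcome of the RCT will be change in systolic BP from baseline to 6-month follow-up". The Primary outcome paragraph names three time points (baseline, 13 weeks, 24 weeks). It adds that "All BP measurements will adhere to a standardized procedure previously used by this study team", and it takes the mean of the last two of three readings at a visit.

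Under Quantitative data Analysis, "Of primary interest is the treatment by time interaction in systolic BP, measured from baseline to 6 months after randomization between TEAM and ETAU". H1 is a repeated measures ANOVA with two groups and three waves, the first being baseline. The listed explanatory variables are age, gender, stroke history and rural or urban status. Neither baseline nor screening SBP is listed as a covariate, and nothing in the document brings an eligibility reading into H1.

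**The concern.** SBP varies from visit to visit, and averaging readings taken minutes apart at one visit does not remove that variation. A pre-randomisation reading from another day carries further information about a participant's usual level, and so can explain part of the variance of the 6-month value. Selection and measurement both precede allocation, so using such a reading as a covariate cannot bias the comparison between arms.

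The stake is precision on the primary contrast. The plan has "power is 0.80 for a clinically significant difference of 10.0 mm Hg between treatment arms", with little to spare, while the sample size section treats reductions as small as 2 mmHg as worthwhile. A narrower confidence interval without extra participants would be useful.

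**Working it through.** **Inputs (Sample size calculations).** A pilot difference "with standard deviation of 25.84, and within subject correlation parameter value of 0.57"; "two-sided test of time-by-treatment group interaction"; "Type I error level is 0.05"; 123 per arm; 25% attrition, so 123 × 0.75 ≈ 92 completers per arm; compound symmetry over the three time periods. The correlation between screening and baseline, r, is not in the document, so it is varied from 0.57 to 0.9. Power is from the noncentral t distribution, and SE = SD × √(2/92).

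**1. The plan's own figure.** Change from a single baseline visit: SD = 25.84 × √(2 × (1 − 0.57)) = 23.96, SE = 3.53, power at 10 mmHg = 0.804. This matches the stated 0.80, so the trial is sized on one baseline visit without screening data.

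**2. Adjust for the existing baseline only.** Residual SD = 25.84 × √(1 − 0.57²) = 21.23, SE = 3.13, power 0.888. This step needs no screening data.

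**3. Add one screening reading as a covariate.** If baseline and screening each correlate 0.57 with month 6, R² = 2 × 0.57²/(1 + r):

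| r | R² | Residual SD | SE | Power |
|---|---|---|---|---|
| 0.57 | 0.414 | 19.78 | 2.92 | 0.927 |
| 0.7 | 0.382 | 20.31 | 2.99 | 0.913 |
| 0.8 | 0.361 | 20.66 | 3.05 | 0.904 |
| 0.9 | 0.342 | 20.96 | 3.09 | 0.896 |

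Against step 2 the SE falls by 7% at best (3.13 to 2.92) and by about 1% at r = 0.9.

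**4. Allow for selection at 140 mmHg.** Eligibility truncates the screening readings. In simulations that apply the plan's SD and correlation before selection, with population means of 140–155 mmHg and two qualifying readings before baseline, the SE falls by about 3–4% with one screening reading and 5–7% with two. If the simulation is instead calibrated so that the selected sample has baseline mean 162.9, SD 25.84 and correlation 0.57, the residual SD goes from 21.24 to 20.02 with one reading (6%) and 19.39 with two (9%). The lower figures are the cautious ones.

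**5. AR(1), which the plan will also consider.** The correlation of screening with month 6 is then r × 0.57. Given baseline, screening carries no further information, and the SE stays at 3.13.

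**6. Two alternatives that do not work as well.**
- *Averaging screening into the baseline value.* Under AR(1) the variance of change is 25.84² × [1 + (1 + r)/2 − 0.57 × (1 + r)], which gives power of 0.790 to 0.801 for r from 0.57 to 0.9, against 0.804 from baseline alone. Because the averaged readings are selected at 140 mmHg or above, it also builds about 2–4 mmHg of regression to the mean into the within-arm change (−3.6 mmHg in the calibrated simulation, using two screening readings).
- *Adding screening only as a main effect to an unadjusted change score.* Under compound symmetry its covariance with the change is 25.84² × (0.57 − 0.57) = 0, so nothing is gained.

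**The case against.** The strongest reply is that the extra readings may not exist in usable form. Criterion 2a does not say who takes the readings or with what device, or whether the baseline visit may count as the second occasion. Participants can be referred by clinical providers, so a clinic value might qualify. The sentence on the standardized procedure sits in the paragraph on the primary outcome, and extending it to eligibility readings is inference. This stands as a condition on the gain. If baseline is itself a qualifying occasion, only one extra reading exists; if no extra reading was recorded, there is nothing to gain.

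A reader might infer that power would rise from 0.80 to about 0.90 or 0.93 by averaging one or two screening readings into baseline. Those figures follow only if compound symmetry is extended to visits the plan does not model. Most of that rise is also available from the existing baseline alone (0.888).

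A reader might likewise take the correlation of 0.57 to mean that 43% of the variance at one visit is noise. The document does not support that. The 0.57 is a pilot mixed-model parameter reported with a 24-week difference, so it can reflect real change and varied response. Readings a few days apart may correlate more highly, which is why r is varied above.

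Finally, a defined baseline visit is a coherent reference, and the plan meets its stated power. That is correct, and it is why the point is minor.

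**Conclusion.** The point holds as a minor loss of efficiency. The plan requires pre-randomisation SBP for eligibility and leaves it out of H1. Nothing here shows bias, a wrong sample size or an invalid test.

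The larger improvement is baseline adjustment (SE 3.53 to 3.13). Screening SBP then adds a modest amount: an SE of 2.92–3.09 with one reading, or about 3–4% off the SE once selection is allowed for (5–7% with two readings), and nothing under AR(1). These figures assume an SD of 25.84 at each visit, a correlation of 0.57 with month 6 (except under AR(1)), 92 completers per arm, and a screening-to-baseline correlation that the document does not give.

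**What to change.** In the analysis plan, before any unblinded analysis, keep the baseline visit as the reference for change. State that the H1 model for 6-month SBP includes two pre-randomisation covariates, handled identically in both arms: baseline SBP, and the recorded pre-baseline screening SBP (the mean if there is more than one). Use only screening values taken with the study's BP procedure, and say whether the baseline visit can serve as a qualifying occasion. Do not average screening into the baseline value; that leaves the planned within-arm changes and time trends as they are.

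The cost is a sentence or two of text and one or two degrees of freedom, with no added visits or participants. If screening values were not kept, baseline adjustment alone still secures most of the gain.
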